how it worked/did not work; **iii)** their thoughts regarding our initial concepts; and **iv)** what they feel would help students use a mobile program. Interviews will employ a semi-structured open-ended approach, allowing for natural conversation with opportunities to explore unanticipated issues. Interviews will be recorded, transcribed, and coded.

The semi-structured interview is expected to last no more than 60 minutes. We will provide a \$100 gift card to the key informants for completion of this interview.

Compensation: Gift cards totaling up to \$120 (\$20-\$30 for each activity and the mini pilot) will be provided to adolescents for completion of Aim 1 activities. Gift cards of \$100 will also be provided to the key informants (school nurse and Vice Principal) and to the school nurses assisting with study activities (e.g., serving as the on-site point person for study recruitment, referring students requesting additional information regarding the study to research staff). There are two nurses at the high school, and we will provide a \$100 gift card per nurse.

See also Section #30, *Consent Process*.

Aim 2

We will recruit from 4-7 local high schools (that were not involved in Aim 1), selected for their high rates of racial/ethnic minorities and low SES status. Prior to recruitment, the study team will obtain IRB approval for the specific schools. To reduce the chances of imbalance across conditions, the schools will be matched based on percentage low income, percentage African American, and number of students, and divided into two sets of two. Within each set of two, we will randomly assign one school to each of the study conditions.

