We will recruit participants with approaches successfully used in our prior school-based studies. Recruitment packets containing an informational brochure, eligibility criteria, and adolescent assent/consent forms will be sent to all students. Flyers and posters will be placed in the school nurse's office and throughout the school. The study will be announced in health education classes and through school-wide class announcements. Recruitment materials will include the Research Coordinator's contact information. After flyers and posters are placed in the school nurse's office and throughout the school, and after the study has been announced in health education classes and through school-wide class announcements, interested adolescents will contact the Research Coordinator to indicate that they are interested in participating in the study. The Research Coordinator will then confirm that the adolescent's parents (or legal guardians) have not indicated that their child may not participate in the study and will schedule a meeting with the adolescent for the earliest possible date. Meetings with the Research Coordinator will take place in the privacy of the school nurse's office. The adolescent will not meet with the school nurse. Informed assent, or informed consent if the student is 18 years of age or older, will be explained such that students understand they have a right to refuse to participate, that their care in the school health clinic and their grades will not be affected by whether or not they decide to participate, and confidentiality will be emphasized. Eligible students will be enrolled and follow the protocol for their school condition. All students in each school will receive the same intervention. Flyers, posters, and announcements will be submitted to the IRB for review and approval prior to use in the study. All recruitment materials will be available in both English and Spanish.

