Aim 2C (Cessation Outcomes) *Hypothesis H2: The intervention will be associated with greater cotinine-validated 7-day point prevalence vaping abstinence rates, lower time to first quit attempt, and less amount of e-cigarette use compared to control at 6-month follow-up.* We recognize that there is some controversy about estimating effect sizes from pilot studies. However, we are calculating effect sizes in our study to provide a range, recognizing that there might be uncertainties because of our small sample size. To estimate effect sizes for V2V intervention versus control, between-condition differences over time will be estimated for **cotinine-validated 7-day point prevalence abstinence** using GEE logistic regression with a random effect for school and fixed effects of condition, time point (baseline and 6 months), and their interaction. Missing data is handled using inverse probability weighting. By taking the repeated measurements into consideration, the GEE model is able to increase the power to test the difference in the outcome. COX regression modeling will be used to examine the intervention effect on **time to first quit attempt** adjusting for other covariates. **Amount of e-cigarette use** will be calculated as a reduction from baseline. We will model this reduction using negative binomial regression modeling if the variance of the distribution of risk reduction is over dispersed.

Other information important for the design of a future study includes standard deviations, as well as **preliminary assessment of possible mediators** such as engagement, behavioral capability, and self-efficacy. We will identify important mediators in exploratory analyses. Guided by the conceptual model based on SCT, we will assess effects of intervention on the mediator and the

effects of the mediator on the outcome, controlling for other mediators in the model, and confounders of the mediator-outcome relationship, and then estimate the proportion of the intervention effect explained. Given the limited sample size, conclusions from the mediation analyses will be limited and treated with caution, but modeling will allow us to explore the constructs of SCT and potential predictors towards a larger RCT.

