- **V2V_Aim 2_Parental Letter_English:** This letter will be sent to all parents (or legal guardians) of grade 9-12 students in the participating schools informing them of the study and asking them to contact us or the school if they do not wish their child to participate. Parents (or legal guardians) will have two weeks from the date the letter is sent to them to contact the study team or school. The Research Coordinator will maintain a list of all parents (or legal guardians) who have contacted the study team or school to indicate that their child may not participate in the study. If parents (or legal guardians) do not contact the study team or school within the two-week timeframe, their child will be eligible to meet with the Research Coordinator to discuss the study. Parental letters and fact sheets will be sent to all parents (or legal guardians) in the top 4-5 languages spoken at each school, including in English and Spanish. We are including the top 4-5 languages so as not to exclude any adolescents from potentially participating in the study based solely on the fact that their parent or parents' (or legal guardians') primary language is a language other than English. We will send a written letter to parents (or legal guardians) to confirm that their opt-out decision has been received and recorded.
- **V2V Aim 2 Parental Fact Sheet:** This fact sheet will be sent to all parents (or legal guardians) of grade 9-12 students at participating high schools. It will contain additional information about the study not included in the parental letters. The fact sheet will be sent in both English and Spanish.
- **V2V Aim 2 Adolescent Assent Form_Intervention and V2V_Aim 2 Adolescent Assent Form_Control:** This assent form will be used with interested adolescents under the age of 18 whose parents (or legal guardians) have not contacted us or their school indicating that they do not wish their child to participate in Aim 2 study activities. Assent will be obtained by the Research Coordinator in the privacy of the school nurse's office. Assent will be explained such that students understand they have a right to refuse to participate, that their care in the school health clinic and their grades will not be affected by whether or not they decide to participate, and confidentiality will be emphasized. We will obtain the adolescent's overt agreement to participate in our study by providing the adolescent with an assent form

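### Students probably volunteer knowing their school's arm, and the abstinence model adjusts for no student-level baseline variable, so self-selection could be read as a V2V effect or could hide one

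*Combined protocol and SAP*

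**What the plan says.** **Allocation.** Section 11 (Aim 2) states that "the schools will be matched based on percentage low income, percentage African American, and number of students, and divided into two sets of two", and then: "Within each set of two, we will randomly assign one school to each of the study conditions". All the matching factors describe schools; none describes the students who join.

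**Recruitment.** Section 11 (Adolescent Recruitment) says "Recruitment packets containing an informational brochure, eligibility criteria, and adolescent assent/consent forms will be sent to all students". After flyers and announcements, "interested adolescents will contact the Research Coordinator to indicate that they are interested in participating in the study". Those who qualify are handled by arm: "Eligible students will be enrolled and follow the protocol for their school condition", and "All students in each school will receive the same intervention". Eligibility in section 6 is any e-cigarette use in the past 90 days, with no requirement to want to quit.

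**Forms.** Section 30 lists "V2V Aim 2 Adolescent Assent Form_Intervention and V2V_Aim 2 Adolescent Assent Form_Control" for students under 18, and separate control and intervention consent forms for those aged 18 or older.

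**Analysis.** Section 13 (Aim 2C) fits abstinence by GEE logistic regression with a school term and "fixed effects of condition, time point (baseline and 6 months), and their interaction". Time to first quit attempt is analysed by Cox regression with adjustment for covariates that are not named. Amount of use is analysed as a reduction from baseline.

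**Data available.** Table 2 collects stage of change, the Hooked on Nicotine Checklist, self-efficacy and past-7-day and past-30-day use at baseline, as well as numbers screened and eligible and the number of and reasons for refusals.

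**The concern.** Randomising schools protects the comparison against differences between schools, to the extent that about four schools can. It does not protect against differences in who volunteers once the offer is known. The two offers differ in kind: a mobile programme with peer coaches, messages and videos, and written materials. With a broad eligibility rule, enrolled students can range from occasional users with no plan to quit to dependent users who are ready.

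If the mix differs by arm, abstinence at 6 months will differ even if V2V does nothing. The abstinence model has no term that could absorb this. H2 is a comparative hypothesis, and its effect sizes are meant to inform a larger trial. A larger sample would not remove the bias, and the same recruitment process could be carried into that trial.

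**Working it through.** **1. What the plan's own figures cover.** The plan gives no readiness share, abstinence rate or calculation for selection. Its sample-size figures concern retention, and they reproduce: design effect 1 + 0.01 × 19 = 1.19; 40/1.19 = 33.6, rounded to 34; exact 95% interval for 29/34 = 68.9% to 95.0%. They are not in question here.

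**2. Is the arm known at enrolment?** Separate intervention and control forms can be handed to the right students only if the school's arm is already fixed. Section 11 puts assent and consent forms in the packet sent to all students, and has enrolled students follow their school's arm. Nothing describes enrolment before allocation, or masking of students or recruiter. The inference is strong, but it remains an inference.

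**3. Size at 6 months if V2V has no effect.** Assumptions, not from the documents: abstinence is 25% among students ready to quit and 10% among the rest.

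Rate in an arm = (share ready × 0.25) + (share not ready × 0.10).

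- Control, 40% ready: 0.4 × 0.25 + 0.6 × 0.10 = 0.160
- V2V, 60% ready: 0.6 × 0.25 + 0.4 × 0.10 = 0.190. Odds ratio = (0.190/0.810)/(0.160/0.840) = 1.23
- V2V, 70% ready: 0.7 × 0.25 + 0.3 × 0.10 = 0.205. Odds ratio = (0.205/0.795)/(0.160/0.840) = 1.35
- Shares reversed (V2V 40%, control 60%): odds ratio = 1/1.23 = 0.81

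A wider grid of assumptions has control 30% ready, V2V 40% to 60% ready, and abstinence if ready / not ready of 15/5, 25/5, 30/10 or 40/5%. It gives spurious differences of 1.0 to 10.5 points and odds ratios of 1.14 to 1.92.

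**4. Size on the planned condition-by-time contrast.** This contrast divides the 6-month odds ratio by the baseline odds ratio.

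- If baseline abstinence is unrelated to readiness, the baseline odds ratio is 1 and the contrast stays at 1.23.
- If baseline abstinence is 15% when ready and 10% when not (assumed), V2V has 0.6 × 0.15 + 0.4 × 0.10 = 0.130 and control has 0.4 × 0.15 + 0.6 × 0.10 = 0.120. The baseline odds ratio is (0.130/0.870)/(0.120/0.880) = 1.10, and the contrast is 1.23/1.10 = 1.12.

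**5. Which adjustment removes it?** Logistic models fitted to the expected proportions, with 60% v 40% ready and baseline abstinence of 15% v 10%:

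| Model | Spurious odds ratio |
|---|---|
| Condition, time, condition × time (as planned) | 1.12 |
| The same plus readiness as a main effect | 1.13 |
| The same plus readiness and readiness × time | 1.00 |
| 6 months only, condition | 1.23 |
| 6 months only, condition plus readiness | 1.00 |

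A baseline covariate entered only as a main effect leaves the interaction almost unchanged, so the form of the adjustment matters. The value 1.00 holds because readiness is the only selection factor in this example.

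**The case against.** **The GEE already includes baseline.** It does, and this can reduce the bias (1.23 to 1.12 in step 4). It removes only a baseline difference in abstinence, not differences in readiness, dependence or intensity of use.

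**This is a feasibility pilot.** Abstinence is a secondary outcome, and section 13 concedes that small samples give imprecise effect sizes. With 34 completers per condition (section 25), 3 points is about one student (0.03 × 34 = 1.02). The standard error of 19% v 16% is √(0.19 × 0.81/34 + 0.16 × 0.84/34) = 0.092, about 9 points before clustering. This stands as a limit on the practical consequence. Imprecision and bias are still different problems, and the plan acknowledges only the first.

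**The direction is unknown.** This is fair. A leaflet-only offer could draw the more motivated students, and the same $25 payment per assessment applies in both arms. The selection could therefore work against V2V.

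**Stronger readings.** A reader might infer that the plan uses no baseline variable anywhere. It does not say that: the Cox model has covariates, though unnamed, and amount of use is measured from baseline. A reader might also infer that a between-arm comparison of retention is biased. No such comparison is planned; retention is estimated within each condition against the 85% target.

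**Much of the reporting is already there.** Table 2 records screening and refusals, and section 13 estimates recruitment rates per condition. What is missing is refusals and baseline profile set side by side by condition.

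**Conclusion.** The point holds for the abstinence GEE. Students very probably choose to join knowing their arm, and the model has no student-level baseline covariate although suitable ones are collected.

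The size cannot be known from the documents. On the assumed rates an intervention with no effect gives a 6-month odds ratio of 1.23 (1.35 with a 70% v 40% split, 0.81 with the shares reversed), and about 1.12 on the planned contrast if baseline abstinence tracks readiness as assumed. It would be too strong to say that allocation is documented as known before enrolment, or that the bias favours V2V; the documents establish neither. The matter is worth correcting because the effect sizes feed the next trial and the analytic correction is nearly free. It does not threaten the primary feasibility aim.

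**What to change.** 1. **Abstinence model.** Estimate the effect from a 6-month model adjusted for baseline stage of change and baseline past-30-day vaping days. Alternatively, keep the GEE and add both covariates with their interactions with time. If events are few, drop to one covariate and keep stage of change, since it measures readiness.
2. **Cox model.** Name the same covariates in place of the unspecified ones.
3. **Reporting.** Tabulate refusals and baseline profile by condition, and state that effect sizes may reflect self-selection.
4. **Order of steps.** State when schools are randomised relative to enrolment. Where feasible, use condition-neutral recruitment materials and complete the baseline survey before disclosing the condition.

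Items 1 to 3 and the statement of order are wording only and use data already collected. The downside is that few events limit the number of covariates, and selection on unmeasured factors remains. Neutral materials and later disclosure are optional and cost more: several assent and consent forms would change, and later volunteers can learn the school's arm from classmates.

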4. OBJECTIVES*

In this study, we will develop Vaper-to-Vaper (V2V), a suite of mobile peer driven tools, including peer texting and coaching, based on lessons learned in our prior tobacco intervention work. These tools will engage and help adolescents use strategies to manage cravings and successfully quit e-cigarettes. The specific aims of the V2V study are to:

Aim 1: Adapt the existing peer-driven and gamification mobile tools to develop the V2V intervention.

1A. Conduct a qualitative study to (1) explore issues unique to e-cigarette use (e.g., concerns, motivations, triggers, symptoms of nicotine dependence), and (2) understand perceived needs for cessation support (preferences for technology (e.g., texting, app-based) to inform adaptation of the toolset.

1B. Work with these users to build the V2V innovations, including peer messaging for adolescents, peer-to-peer videos, and game narratives for gamification.

1C. Refine the V2V mobile toolset with iterative usability testing (mini-pilot).

There are no hypotheses for Aim 1. Aim 1 is just to adapt the existing peer-driven and gamification mobile tools to develop the V2V intervention.

Aim 2: Evaluate the feasibility of the research protocols and the feasibility and acceptability of the V2V intervention (peer messaging, peer coaching, and gamification) compared to e-cigarette cessation written materials (control) in a pilot feasibility study.

2A. Assess the feasibility of the research protocols, including participant recruitment and retention.

***Hypothesis H1:** We will be able to recruit 80 adolescents (20/school, 40 per study condition), and $\geq 85\%$ will be retained in each study condition at 6-month follow-up.*

2B. Monitor V2V engagement (e.g., number of responses to texting quizzes, peer coaching interactions, peer videos viewed) and assess acceptability of and satisfaction with the program.

2C. Assess preliminary effect size estimates of the V2V intervention on cotinine-validated 7-day point prevalence abstinence, time to first quit attempt, and amount of use.

***Hypothesis H2:** The intervention will be associated with greater cotinine-validated 7-day point prevalence vaping abstinence rates, lower time to first quit attempt, and less amount of e-cigarette use compared to control at 6-month follow-up.*

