5. BACKGROUND*

Adolescent e-cigarette use has now exceeded combustible cigarette use, leading the FDA and the U.S. Surgeon General to call the increasing use of e-cigarettes among U.S. adolescents an epidemic.¹⁻⁴ The 2018 National Youth Tobacco Survey found a 78% increase in e-cigarette use in just one year,⁵ with over 3.5 million youth currently using e-cigarettes. Alarmingly, 28% of high school e-cigarette users are vaping on 20 or more days in the past month.⁵ The high amounts of nicotine in e-cigarettes harm adolescent brain development, impacting learning,

memory, attention, mood, and impulse control.⁶ Further, adolescent e-cigarette users are at higher risk than non-users of transitioning to traditional cigarettes.^{1,2,6-10} Tobacco use continues to be the leading cause of preventable morbidity and mortality in the U.S., with nearly all tobacco use beginning during youth and young adulthood.^{11,12} Once transitioned, 80% of these adolescent smokers will continue to smoke into adulthood and, of those, one-half will die 13 years earlier than nonsmoking peers.^{13,14}

Evidence-based and accessible e-cigarette cessation interventions are critically needed to help adolescent e-cigarette users quit.^{1,2,7} To our knowledge, there are currently no evidence-based interventions to assist adolescent e-cigarette users in quitting.^{1,2,7} E-cigarette users are a complex group, including all race and ethnic groups as well as youth of higher and lower socioeconomic status (SES).¹⁵ Although recent concerns regarding vaping and proposed regulatory changes (increasing purchasing age, banning flavors) may increase adolescent interest in quitting and demand for e-cigarette cessation interventions, the perception of lower risk of e-cigarettes may lead to a lower intention to quit,^{16,17} with the majority of youth e-cigarette users believing vaping only includes flavoring and not nicotine.¹⁸ Therefore, novel approaches specifically tailored to their unique needs that can be disseminated broadly are required to engage, educate, motivate, and support adolescent e-cigarette users to successfully quit.

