6. INCLUSION AND EXCLUSION CRITERIA*

Aim 1 Study Population (20 adolescent e-cigarette users (Peer Advisory Panel) and two key informants)

The study population will be derived from 20 adolescent e-cigarette users in one high school selected for its high rate of racial/ethnic minorities and low SES status. We will also recruit two key informants (school nurse and Vice Principal) from the same high school.

Inclusion criteria for peer advisory panel: (1) enrolled in grade 9-12 at a local high school; (2) current e-cigarette user; (3) have a smartphone; and (4) English- or Spanish-speaking. Current e-cigarette user is defined as a response greater than “0 days” to the question: “During the past 90 days, on how many days did you use e-cigarettes?” This eligibility criterion is modeled on a question in the 2018 National Youth Tobacco Survey (NYTS), a survey of U.S. middle and high school students which used a 30-day timeframe.

Exclusion criteria for peer advisory panel: (1) unable or unwilling to provide informed assent or consent (in the case of those aged 18 years or older).

Inclusion criteria for two key informants: (1) employed as a school nurse or Vice Principal at the Aim 1 high school.

Exclusion criteria for two key informants: (1) unable or unwilling to participate in the study.

Aim 2 (80 adolescent e-cigarette users and up to 12 key informants)

In Year 2 of the project, 80 adolescent e-cigarette users in 4-7 high schools selected for their high rates of racial/ethnic minorities and low SES status (20/school, 40/study condition) will be recruited and complete assessments at baseline and 6-month follow-up.

Inclusion criteria for 80 adolescent e-cigarette users: (1) enrolled in grade 9-12 at a participating high school; (2) current e-cigarette user; (3) have a smartphone; and (4) English- or Spanish-speaking. Current e-cigarette use is defined as a response greater than “0 days” to the question: “During the past 90 days, on how many days did you use e-cigarettes?” This eligibility criterion is modeled on a question in the 2018 National Youth Tobacco Survey (NYTS), a survey of U.S. middle and high school students which used a 30-day timeframe.

Exclusion criteria for 80 adolescent e-cigarette users: (1) unable or unwilling to provide informed assent or consent (in the case of those aged 18 years or older).

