With participant permission, we will collect complete and accurate contact information from the student at baseline, including home address, phone, cell phone, email, and phone numbers of three contacts and best times and days to reach them to maximize retention. A contact sheet will be completed by the participant that will include the above information. Care will be taken to maintain the confidentiality of the student's participation; therefore all students will be asked to provide us with the individuals or contact information where they feel comfortable being contacted by study staff or where they feel assured that the confidentiality of their participation will be maintained. The other contacts provided by the student will not be informed of the student's vaping status. We have found in prior studies that cell phone numbers and e-mail addresses are particularly helpful in remaining in contact with this population. Tracking procedures will be implemented for any student who does not attend a scheduled study visit or who is not accessible by telephone or e-mail at the contact location provided. Attempts to locate students will be made mainly through the schools and by telephone calls to the contacts provided or directory assistance.

Table 2. Study Assessments, Measures and Data Collection Timing

Variable and Measure	Relevant Aim	Baseline	6-month follow-up
Recruitment: # screened and eligible, # and reasons for refusal	2A	•	
Retention: # of dropouts, reasons for dropping out	2A		•
Engagement (V2V only): # of completed responses to texting quizzes, peer videos viewed, peer coaching interactions	2B		*
Acceptability and satisfaction: Client Satisfaction Questionnaire (CSQ-8) semi-structured interview	2B		•
Cotinine-validated 7-day point prevalence abstinence: saliva samples collected from all; analyzed for those reporting 7-day abstinence; cut-off 11.4 ng/ml	2C		•
E-cigarette use frequency (past 7 and 30 day) and intensity (# days and amount vaped in past 7 and 30 day)	2C	•	•
THC/marijuana and other tobacco use frequency (past 7 and 30 day) and intensity (# days and amount vaped)		•	•
Social Cognitive Theory (SCT) constructs			
Self-efficacy, confidence to quit: Self-efficacy Questionnaire (SEQ-12)		•	•
Demographics and tobacco use			
Demographics: age, gender, socio-economic status, race/ethnicity, grade in school, academic performance		•	•
History of all tobacco use, past and recent quit attempts, cessation strategies used		•	

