Data collection: Data collected from participants will be obtained through interviews, paper and pencil surveys, and collection of saliva samples for cotinine assessment by the Research Coordinator in-person at the school nurse office at baseline and 6-months post-study entry. The student survey and assessment tools for this study will be adapted from our prior adolescent smoking cessation trials and will be submitted to the IRB for review and approval prior to use in the study. Survey and assessment tools are described in Table 2 on page 10 of the ISP. Data confidentiality will be emphasized on the surveys and verbally by the Research Coordinator (see section #30), and by the use of a unique identification number. Data will be entered into the regulated environment through a secure Research Electronic Data Capture (REDCap) form. REDCap is a secure web application for building and managing online surveys and databases that was funded by the National Institutes of Health. REDCap data is also stored in a regulated environment. These files will be deleted after study completion. Portable devices used to collect data (audio and film recordings) will be UMMS-issued devices and files will not be encrypted during the recording, but the recordings will be transferred as soon as possible (i.e.: typically within the same day) to UMMS servers. Once the files are transferred, they will be deleted from the portable devices.

We will conduct biochemical verification using a saliva NicAlert® test (Nymox Corporation), which is a semi-quantitative method that uses a dipstick to measure the level of cotinine in a sample of saliva. The test strip displays the result in seven zones with each zone representing a range of levels of cotinine/smoking (e.g.: zone 0 [0 – 10 ng/mL, a nonsmoker] to zone 6 [>1000 ng/mL, a heavy smoker]). The results are read as 0-6, and as recommended, any value ≥ 1 is considered as tobacco use. Research staff will enter these values into the database, using the participant ID as an identifier, and destroy the samples.

Data Analysis:

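### Cotinine cannot tell vaping from other tobacco, so a student who has stopped vaping can be scored as not abstinent from vaping; the other-tobacco answers already collected are not used to identify these students

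*Combined protocol and SAP*

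**What the plan says.** - **Outcome.** H2 (section 4, repeated in section 13) expects "greater cotinine-validated 7-day point prevalence vaping abstinence rates" in the intervention arm. Section 10 makes abstinence a secondary outcome, to be reported as a preliminary effect size. The primary outcome is feasibility.
- **Validation.** For the abstinence outcome, Table 2 in section 11 has "saliva samples collected from all; analyzed for those reporting 7-day abstinence; cut-off 11.4 ng/ml". Section 13 names the NicAlert strip, describes its zones by level of smoking, and states that "any value ≥ 1 is considered as tobacco use". The sample is destroyed once the reading is entered.
- **Eligibility.** Section 6 sets no condition on other tobacco. It reads "Exclusion criteria for 80 adolescent e-cigarette users: (1) unable or unwilling to provide informed assent or consent", and that is the only exclusion.
- **Expected other-tobacco use.** Section 5 notes that "adolescent e-cigarette users are at higher risk than non-users of transitioning to traditional cigarettes". Table 2 has a row for "THC/marijuana and other tobacco use frequency (past 7 and 30 day) and intensity (# days and amount vaped"), collected at both visits.
- **Analysis.** The abstinence model in section 13 is a logistic GEE with school and "fixed effects of condition, time point (baseline and 6 months), and their interaction". No rule, covariate, subgroup or sensitivity analysis for abstinence refers to other tobacco. The Cox model for time to first quit attempt adjusts for covariates, but these are not named.

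**The concern.** The outcome's name and its scoring describe different things. The name is abstinence from vaping. A positive strip shows nicotine exposure from some tobacco product and does not show which one. A student who has stopped vaping but smokes can fail the test on the cigarettes alone.

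The survey is not in the documents, but its wording does not remove the problem. If the abstinence question covers vaping only, the student says yes and the strip can overturn the answer. If it covers all tobacco, the student says no and the saliva is not analysed. In both cases the student is not counted as abstinent.

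V2V and the control materials are both aimed at e-cigarettes, so the effect on vaping is what a later trial would want from Aim 2C. The cessation outcome is also set against the engagement score in Aim 2B. Schools are allocated within matched sets, but "the schools will be matched based on percentage low income, percentage African American, and number of students", so the matching does not address tobacco use.

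**Working it through.** **The plan's own figures.** The documents give no abstinence rate and no rate of other-tobacco use, so there is no stated figure to reproduce on this point. The number of completers is 40 × 0.85 = 34 per condition, as in section 25.

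**Set-up.** Let q be an arm's true proportion abstinent from vaping. Let s be the share of those quitters who are cotinine-positive from other tobacco. Then

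validated rate = q × (1 − s).

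One affected student lowers an arm's rate by 1/34 = 2.9 percentage points.

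**Equal s in both arms.** The risk difference becomes (1 − s) times its true value. The factor cancels from the risk ratio. The odds ratio, which the planned logistic model estimates, changes little. The values of q below (15% control, 30% V2V) and of s are assumptions for illustration:

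| s | Control | V2V | Risk difference (points) | Risk ratio | Odds ratio |
|---|---|---|---|---|---|
| 0% | 15.0% | 30.0% | 15.0 | 2.00 | 2.43 |
| 10% | 13.5% | 27.0% | 13.5 | 2.00 | 2.37 |
| 20% | 12.0% | 24.0% | 12.0 | 2.00 | 2.32 |
| 40% | 9.0% | 18.0% | 9.0 | 2.00 | 2.22 |

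For example, at s = 40% the odds ratio is (0.18/0.82) / (0.09/0.91) = 2.22.

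**Different s by arm.** The risk ratio is multiplied by (1 − s in V2V)/(1 − s in control). With the same assumed q:

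- s = 10% in control and 30% in V2V: 13.5% versus 21.0%, difference 7.5 points, odds ratio 1.70 (risk-ratio factor 0.7/0.9 = 0.78).
- s = 30% in control and 10% in V2V: 10.5% versus 27.0%, difference 16.5 points, odds ratio 3.15 (risk-ratio factor 0.9/0.7 = 1.29).

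The true odds ratio is 2.43 in both cases.

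**What a sensitivity analysis can bound.** Call group (a) the self-reported vaping abstainers who read 1 or more and report other tobacco in the past 7 days. Take a hypothetical result with 34 per arm: 8 validated abstainers in V2V, 4 in control, and 3 group (a) students in each arm.

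- Group (a) abstinent in neither arm: (8 − 4)/34 = 11.8 points.
- Group (a) abstinent in both arms: (11 − 7)/34 = 11.8 points.
- Group (a) abstinent in control only: (8 − 7)/34 = 2.9 points.
- Group (a) abstinent in V2V only: (11 − 4)/34 = 20.6 points.

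The first two runs bound each arm's rate but give the same difference. The range for the between-arm effect comes from the last two.

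**The case against.** The strongest reply is that this matters little here. Abstinence is secondary. Section 13 says a pilot this small cannot estimate effects meaningfully, sizes the study on retention, and offers effect sizes only as a range. With equal misclassification the planned odds ratio barely moves. An endpoint of abstinence from all tobacco is legitimate, and section 10 lists tobacco use among the secondary outcomes, so those data may be reported. All of this stands, and it limits the weight of the point. But sampling error does not settle which behaviour was measured, and nothing in the plan links the tobacco data to abstinence.

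The protocol also does not say in words that a positive strip overrides self-report. That is inferred from the term cotinine-validated together with the cut-off.

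A reader might infer more than the documents support:

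- *Every recent smoker will test positive.* Zone 0 runs to 10 ng/mL and Table 2's cut-off is 11.4 ng/ml, so light or occasional use may read 0. Only use that is recent and heavy enough counts towards s.
- *A chance of arm imbalance can be computed from 34 completers and the plan's intra-school correlation of 0.01.* The relevant group is vaping quitters, not all completers, and the documents give no correlation for other-tobacco use.
- *A conflict with the amount-of-use outcome is itself a defect.* A self-reported amount and a validated status can differ by design.

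**Conclusion.** The point holds as a mismatch between label and scoring in a secondary, preliminary outcome. As written, the plan can count a true vaping quitter as not abstinent from vaping, and it does not use the data that would show how often this may have happened.

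The size cannot be fixed from the documents; every value of s and q above is an assumption. With equal s, the risk difference shrinks in proportion, while the odds ratio falls from 2.43 to 2.22 even at s = 40%. With unequal s, the estimate can be too low or too high.

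A reader might infer that the effect of V2V will be materially understated, or that the trial's main result is at risk. The documents support neither: the direction depends on an unknown difference between arms, and recruitment and retention are untouched.

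**What to change.** 1. Label the planned outcome cotinine-validated abstinence from e-cigarettes and other tobacco.
2. Make the self-reported 7-day abstinence question ask about e-cigarettes only.
3. Report, by condition, the self-reported vaping abstainers with NicAlert 1 or more, split by whether they report other tobacco in the past 7 days. Where they do, vaping status cannot be verified; where they do not, the claim of abstinence is unsupported.
4. Add a sensitivity estimate that counts those reporting other tobacco as abstinent from vaping in both arms. State that, for this source of error and if other-tobacco reports are truthful, it and the planned estimate bound each arm's rate but not the between-arm effect.
5. To bound the effect, repeat the estimate counting this group as abstinent in V2V only, then in control only.

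The cost is a few sentences, a check of one survey item and three extra model runs. Saliva and the past-7-day other-tobacco answers are already collected at 6 months. Since samples are destroyed after reading, the split should be specified beforehand. The sensitivity estimates rely on self-report for this group, so they should accompany the validated outcome and not replace it.
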